8.7. Physical Examination

A routine physical examination will be performed at Screening and Follow-Up Visits. Abnormal and clinically significant findings in physical examinations will be reported and summarized as Medical History or Adverse Events, as appropriate.

8.8. Neurological Examinations

A neurological examination will be administered at Screening and Follow-Up Visits. Neurological examination findings will be summarized for eye movements, facial sensations, motor function strength, sensory, reflexes, plantar response, cerebellar function / coordination by

visit, dose level and overall. Neurological examination findings shift from baseline visit to post-baseline visit will also be tabulated.

Individual neurological examination findings will be listed for each test chronologically by patient ID, visit, and the actual assessment date and time.

8.9. Ashworth Score

Ashworth score will be assessed at all study visits. Summary statistics of the Ashworth total score at each study visit will be tabulated. A list will be provided with the actual assessment date and answers to all the questions.

8.10. Beck Depression Inventory Fast Screen Version

The BDI-FS will be assessed at all study visits. Summary statistics of the BDI total score will be provided for each assessment time point by dose level and overall. A list will be provided with the actual assessment date and answers to all questions.

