8.3.2. Safety Endpoints

The safety endpoints are listed in the following:

- The incidence and severity of TEAEs
- Clinically important changes in safety assessment results [including, as appropriate, vital signs, clinical laboratory tests, ECGs, Ashworth score, falls assessment, physical and neurological examinations, BDI-Fast Screen and suicidality assessment].

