2.2.5. Safety Endpoints

The safety endpoints are listed in the following:

- Incidence and severity of treatment-emergent adverse events (TEAEs)
- Clinically important changes in safety assessment results [including, as appropriate, vital signs, clinical laboratory tests, ECGs, Ashworth score, falls assessment, physical and neurological examinations, beck depression inventory and suicidality assessment]

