5.5.10.5. Beck Depression Inventory

The Beck Depression Inventory (BDI[®]) – Fast Screen (BDI-FS) is a shortened version of the BDI-II that evaluates key symptoms of depression. It was developed to factor out co-occurring depression symptomatology that may be related to a medical condition ([Steer 1999](#)), and concentrate on factors of depression that relate solely to depression. The BDI-FS contains 7 self-reported items that evaluate major depressive symptoms over the past 2 weeks, including sadness, pessimism, past failure, loss of pleasure, self-dislike, self-criticalness, and suicidal ideations ([Beck 2000](#), [Steer 1999](#)). Individual scale items are scored on a 4-point continuum (0=least, 3=most), with a total summed score range of 0–21. Higher scores indicate greater depressive severity. Patient's depression level will be classified using the BDI total score as shown in [Table 5](#). The BDI total score will be set to missing if an answer to any of the 7 items is missing.

Table 5: Depression Level Classification by BDI Total Score

Depression Level	BDI Total Score
Minimal Depression	0 - 3
Mild Depression	4 - 6
Moderate Depression	7 - 9
Severe Depression	10 - 21

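### The listed suicidality assessment has no by-dose summary: its only scheduled measure, one BDI-FS item, is tabulated only inside the total score

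*SAP*

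**What the plan says.** Both documents define a safety endpoint of clinically important changes in safety assessments, followed by a bracketed list that applies as appropriate. In Protocol 8.3.2 the list ends with "BDI-Fast Screen and suicidality assessment"; in SAP 2.2.5 it ends with "beck depression inventory and suicidality assessment". In both, suicidality stands beside the depression inventory, not inside it.

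Neither schedule of events (Appendix A of each document) contains a suicidality instrument, and Protocol 5.13 describes none. SAP 5.5.10.5 gives the BDI-FS items as "sadness, pessimism, past failure, loss of pleasure, self-dislike, self-criticalness, and suicidal ideations", so suicidal ideation is one of seven. On scoring it says: "Individual scale items are scored on a 4-point continuum (0=least, 3=most), with a total summed score range of 0–21". It also says: "The BDI total score will be set to missing if an answer to any of the 7 items is missing". Table 5 of the SAP classes totals of 0–3 as minimal depression.

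For analysis, SAP 8.10 states: "Summary statistics of the BDI total score will be provided for each assessment time point by dose level and overall". It adds a listing with the answers to all questions. Protocol 8.4.5.10 likewise summarises only the total, as value and change from baseline.

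**The concern.** Every other assessment in the bracketed list has its own SAP section: laboratory data, vital signs, ECG, physical and neurological examination, Ashworth score, BDI-FS and falls (SAP 8.4 to 8.11). Suicidality has none, and SAP 12 records no decision to drop it. Followed as written, the plan produces no count of patients with suicidal ideation by dose group.

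The item does enter the BDI-FS total, but a mean of totals is a poor place to look for it. One item contributes at most 3 of 21 points, and an uncommon event in a few patients is averaged over the whole arm. The missing-item rule adds a second loss: a patient who endorses suicidal ideation but skips any other question contributes nothing to that visit's summary, although the relevant answer was given.

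At stake is the ability to see, in a dose-ranging trial meant to guide later dose selection, whether this safety measure changes with dose.

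**Working it through.** **1. Score range.** Seven items scored 0–3 give 7 × 0 = 0 to 7 × 3 = 21, which reproduces the range in SAP 5.5.10.5. The suicidal-ideation item is at most 3 of the 21 points. The maximum answer on that item with zero on the other six gives a total of 3, inside the 0–3 band of Table 5.

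**2. Where the item appears in planned output.**
- BDI-FS summary tables (SAP 8.10): total only.
- BDI-FS listing (SAP 8.10): every answer, by patient. Listings show the assigned dose level and are sorted by treatment (SAP 5.1), without counts or denominators by arm.
- Adverse-event tables (SAP 8.1.1, 8.1.2): by preferred term and dose, but only if the investigator reports an event.

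The listing could hold up to about 445 patients × 7 visits = 3,115 answers to this one item.

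**3. Dilution, illustrated.** From the documents: 445 randomised 1:1:1:1, so 445 / 4 ≈ 111 per arm. Assumed, because the documents give no values: emergent ideation in 5% on one dose and 1% on placebo; a 2-point rise on the item in those patients; no change in the other six items; SD of the total between 1.5 and 3.5.

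- Shift in mean total: (0.05 − 0.01) × 2 = 0.08 points.
- Standard error of a difference between two arms: SD × √(2/111).

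| Assumed SD | Standard error | 0.08 / standard error |
|---|---|---|
| 1.5 | 0.20 | 0.40 |
| 3.0 | 0.40 | 0.20 |
| 3.5 | 0.47 | 0.17 |

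- Expected patients: 111 × 0.05 = 5.6 and 111 × 0.01 = 1.1, so about 6 versus 1.

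**4. What the count would show.** Fisher's exact test on 6/111 versus 1/111 gives a two-sided p of 0.12. A reader would see the imbalance, but it would not be conclusive.

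**5. A more extreme case.** Suppose 5% of one dose arm move from 0 to 3 on the item and none do on placebo. The mean total shifts by 0.05 × 3 = 0.15 points. Approximate power at two-sided 0.05 is 5–11% on the mean total, Φ(0.15/SE − 1.96), for SD 3.5 down to 1.5. On the proportion it is about 67%, from the usual normal approximation for two proportions. With the same 5-point excess over a placebo rate of 1% or 2% (6% versus 1%, 7% versus 2%), power on the proportion is 53% and 44%. The count is the more sensitive summary in each case, without being decisive.

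**The case against.** The strongest reply is that the information is not lost. SAP 8.10 lists every answer, and the listing can be read by arm. Suicidality reported as an adverse event is tabulated by dose, as are serious events and events leading to discontinuation or death. A data monitoring committee reviews safety unblinded (Protocol 5.16) and may ask for more data (SAP 4.1). Patients judged a suicide risk are excluded at entry. Suicidality is one entry in a qualified list, not a stand-alone endpoint. Table shells, kept separately under SAP 5.3, might include the item.

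Much of this stands, and it rules out three stronger readings that a reader might infer:

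- **That a dose signal would be missed.** The listing and the adverse-event tables are real routes to it. They are weaker than a table: one needs reading by eye, and the other depends on the investigator. Protocol 7.2 elicits events with two general questions, and neither document makes a positive answer to this item an adverse event.
- **That the minimal-depression label hides the worst case.** The arithmetic is right, but Table 5 grades depression, and SAP 8.10 specifies no table by its categories. The example also needs zero on all six other items, a pattern the documents give no reason to expect.
- **That a skipped item removes the patient from the table.** The rule sets only that visit's total to missing. The patient still contributes at visits with a complete form. The documents give no rate of skipped items.

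The entry exclusion lowers prevalence at baseline but does not address emergence on treatment. Possible content in unseen shells does not replace a definition in the SAP.

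**Conclusion.** The point holds as a gap in the safety analysis. A suicidality assessment is named in both documents, its only scheduled source is one BDI-FS item, and no by-dose tabulation of that item is specified. A change confined to the item could be diluted in the total or overlooked, and finding it would then rest on listings or adverse-event reports.

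The size is illustrative only. At 5% versus 1% with a 2-point rise, the total moves by about 0.2 standard errors at SD 3 and 0.4 at SD 1.5, against a count of about 6 versus 1. If other items rose along with suicidal ideation, the total would move more and the dilution would be less. No efficacy conclusion is affected.

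**What to change.** In SAP 5.5.10.5, state that the suicidality assessment named in SAP 2.2.5 is the BDI-FS suicidal-ideation item. In SAP 8.10, add a descriptive table with:

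- the number and percentage scoring ≥1 and ≥2 on the item, by visit and dose group;
- the number and percentage whose item score worsens from baseline at any post-baseline visit, by dose group.

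Use the item whenever it is answered, even if the total is missing, with patients answering the item as the denominator. Present it separately from the Table 5 depression levels.

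The cost is one more safety table. The data are already collected at every study visit, so no assessment is added. The counts will be sparse and should be read descriptively, without a formal test.

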8.11. Fall Assessment

The fall assessment will be conducted at all study visits except Screening. The number and percent of patients with one, two, three, four or more falls, with answers to the activities engaged at the time of fall, physical symptoms immediately preceding the fall, and whether resulting injury will be tabulated. A list will be provided with the actual assessment date, and answers to all questions.

8.12. Study Termination Status

Number and percentage of patients who completed or prematurely discontinued planned study dosing, and reasons of premature discontinuation will be tabulated. For patients who discontinued prematurely, the date and reason of premature discontinuation will be listed.

9. PHARMACOKINETIC AND PHARMACODYNAMIC ANALYSES

9.1. Pharmacokinetic Analyses

PK analysis will be performed based on the PKS. All of the PK samples collected, including those obtained at Hours 0, 1, 3 on Day 1 as well as Hours 0, 1, 3 and 6 at Week 2 and Week 12 from patients enrolled prior to Amendment 03, will be used for PK analyses. Descriptive statistics in terms of mean, SD, geometric mean, coefficient of variation (CV), geometric CV, median, and range will be provided for concentrations at all planned sampling time points. Geometric mean concentrations over time will be graphically displayed.

For each patient enrolled prior to Amendment 03, the PK parameters t_{max} , C_{max} and AUC_{12} at Week 2 and Week 12 will be calculated based on the plasma concentrations of reldesemtiv, its metabolites and riluzole using non-compartmental PK methods. The PK parameters t_{max} , C_{max} on Day 1 for patients enrolled prior to Amendment 03, and C_{trough} at Week 2 and Week 12 for all

patients will be calculated based on the plasma concentrations of reldesemtiv, its metabolites and riluzole. The PK parameters listed above will also be summarized by dose level.

Dose proportionality will be examined using the power model approach based on C_{trough} . The relationship between the PK parameter, C_{trough} and dose can be described by the following power model:

$$\ln(C_{\text{trough}}) = \alpha + \beta \times \ln(\text{dose}) + \varepsilon$$

where α and β are the intercept and slope of the modeling equation, and ε represents the error term. A tentative conclusion of dose-proportionality will be made if the 90% CI for the slope includes 1.

The attainment of steady-state of reldesemtiv following multiple doses will be verified using a linear regression model for log-transformed trough concentrations on sample collection time by dose group. Since the first post baseline PK sample is collected at Week 2, the trough concentrations starting from Week 2 and beyond will be included in the model. If the 90% confidence interval (CI) of the slope from the model contains zero, steady state will be concluded as attained at no later than Week 2.

Selected PK parameters (eg, AUC_{12} , C_{max} and C_{trough} at Week 12) between patients who took reldesemtiv alone and those who took reldesemtiv plus edaravone will be compared. The natural log-transformed least square mean difference and the associated 90% CI will be calculated using a linear regression model that includes model terms of dose level, edaravone use status at baseline, and interaction of dose level by edaravone use status. An unstructured covariance matrix will be used for the model. Back-transformation will provide point estimates and 90% CIs for the geometric mean ratio that indicates the magnitude of drug interaction. Summaries of selected PK parameters will be presented graphically by dose level, as appropriate.

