5.12. Pharmacokinetic Sampling

Blood samples for analysis of CK-2127107, its metabolites, and riluzole will be collected from patients at the nominal time points listed in [Table 3](#).

Table 3: Pharmacokinetic (PK) Samples

Day	Sample Time Points
Day 1	Pre-dose and 1 (\pm 15 min) hour post-dose
Week 2	Pre-dose and 1 (\pm 15 min) hour post-dose
Week 4	Pre-dose
Week 8	Pre-dose
Week 12	Pre-dose and 1 (\pm 15 min) hour post-dose

If an indwelling catheter is used, saline flushes will be used. In some cases, sites may be unable to obtain the 6 hour timepoint at Week 2 or Week 12 for logistical reasons; these cases should be discussed with the medical monitor preferably ahead of time.

After completion of bioanalysis, remaining plasma samples will be retained consistent with the Sponsor's standard operating procedures. These samples will not be used for pharmacogenomic testing.

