6.3. Dosing Diary

A dosing diary will be maintained by the patient to record date and time of twice daily study drug administration. The dosing diary should be returned at each clinic visit.

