5.5.11. Pharmacokinetics Parameters

The PK parameters are defined as follows:

Parameter	Definition
AUC_{0-t}	Area under the concentration-time curve from time zero to the last measurable concentration, also called AUC_{last} .
$AUC_{0-\tau}$	Area under the concentration-time curve from time zero to time τ (eg, hours). It is calculated by using the trapezoid rule if all concentrations are above quantitation limit before time τ , and by using extrapolation if concentration drops below quantitation limit before time τ .
C_{max}	The maximum (or peak) concentration that a drug achieves in tested area after the drug has been administrated and prior to the administration of next dose.
C_{trough}	The minimum concentration between dose time and dose time + τ (at T_{trough}).
t_{max}	The time that C_{max} was observed.

The parameters C_{max} , AUC and t_{max} will be derived using the following rules:

- For calculation of C_{max} , pre-dose value will not be included in the determinations.
- Analyses will be based on actual sampling time converted to elapse time defined as time from dosing.
- Any concentration below the lower limit of quantitation (LLOQ) will be reported as 0.00 for summaries by each time point.
- For AUC calculations, samples with values below the LLOQ prior to the first measurable concentration will be set to zero. Samples with below the LLOQ result after the first measurable concentration will be treated as missing and the calculation of AUC will proceed by fitting a trapezoid between the surrounding, non-missing values.
- t_{max} will be calculated only for patients who have at least two samples collected after dosing.

At Weeks 2 and 12 PK samples will be collected at pre-dose, and 1, 3 and 6 hours post-dose. For AUC₁₂ calculation, the pre-dose concentration will be used to approximate the concentration value at 12 hours.

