8.3. Concomitant and Other Medications

Concomitant medications reported on the eCRF will be summarized for the safety analysis set. See [Section 5.5.10.4](#) for the definition of concomitant medications. Medications with a start date that is 28 days after the last dose of the study drug will be excluded from the summary. The World Health Organization Drug dictionary will be used to classify medications by therapeutic class (ATC Class 3) and preferred name. If ATC Class 3 is not available, ATC Class 2 will be used in the summary. Coding will be performed using WHO Drug Dictionary Enhanced with Herbal Dictionary, B2, March 2017.

The number and percentage of patients who received concomitant medication will be summarized by dose level, therapeutic class and preferred term (using ATC Class Level III). Multiple drug usage by a patient will be counted only once in each category.

CYP3A4 strong inhibitors that should be avoided from 7 days before the start of dosing through the last day of dosing. CYP3A4 strong inducers that should be avoided from 14 days before the start of dosing through the last day of dosing. OCT1/OCT2 substrates that should be avoided from 7 days before the start of dosing or should be used with caution during the trial. Patients who take CYP3A4 strong inhibitors, CYP3A4 strong inducers, or OCT1/OCT2 substrates prior or during the study treatment will be listed.

In addition, a listing of concomitant medication with start/stop date, days relative to the start of therapy, dose / unit / route / frequency, indication and purpose of all medications taken from screening through the end of study will be provided.

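### SAP 9.1 derives riluzole tmax, Cmax, AUC12 and Ctrough from samples timed to the study drug dose, and neither document specifies a riluzole time origin

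*SAP*

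**What the plan says.** SAP 9.1 has two parameter sentences that include riluzole.

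- **Patients enrolled before Amendment 03:** tmax, Cmax and AUC12 at Weeks 2 and 12 are "calculated based on the plasma concentrations of reldesemtiv, its metabolites and riluzole using non-compartmental PK methods". The next sentence adds tmax and Cmax on Day 1 for these patients.
- **All patients:** the same second sentence adds Ctrough at Weeks 2 and 12, also for riluzole; its closing words and the start of the sentence after it are "patients will be calculated based on the plasma concentrations of reldesemtiv, its metabolites and riluzole. The PK parameters listed above will also be summarized by". All these parameters are then summarised by reldesemtiv dose level.

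Protocol 5.12 uses one sample set and one timetable for every analyte: "Blood samples for analysis of CK-2127107, its metabolites, and riluzole will be collected from patients at the nominal time points" in its Table 3. The visit sections place those samples before the study drug dose and, on Day 1 and at Weeks 2 and 12, 1 h after it. Patients enrolled before Amendment 03 also had samples at 3 h on Day 1 and at 3 and 6 h at Weeks 2 and 12.

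SAP 5.5.11 has a single clock: "Analyses will be based on actual sampling time converted to elapse time defined as time from dosing". It leaves the pre-dose value out of Cmax and reuses that value as the 12-hour concentration in AUC12. It gives no separate rule for riluzole.

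The only dose times the protocol asks patients to record are for study drug: "A dosing diary will be maintained by the patient to record date and time of twice daily study drug administration" (Protocol 6.3). The SAP's output for other drugs is "a listing of concomitant medication with start/stop date, days relative to the start of therapy, dose / unit / route / frequency" (SAP 8.3), without a time of intake. Inclusion criterion 11 requires riluzole users to have been on it for at least 30 days before screening, but sets no time of day.

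**The concern.** Riluzole is background medication, already established before Day 1. Nothing in either document makes a patient take it with the clinic dose of study drug, or hold it until the pre-dose sample is drawn. A pre-dose sample is therefore pre-dose for reldesemtiv but may fall anywhere in the riluzole interval.

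Suppose a patient took riluzole at home 2 h before the clinic dose. The pre-dose sample is then closer to a riluzole peak than to a trough. Under the rules as written it is barred from Cmax, it stands in for the 12-hour value in AUC12, and on the abbreviation-list definition it is reported as Ctrough. The reported tmax is counted from the wrong dose.

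At stake is a set of riluzole parameters, tabulated by reldesemtiv dose level, whose names promise more than the data can support. Timing scatter would also widen the spread within each dose group.

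**Working it through.** The plan states no figure on this point, so there is none to reproduce. The check is a comparison of the texts followed by two illustrations.

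**1. Which parameters need a riluzole clock**

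| Riluzole parameter | Who | What it needs | What the documents give |
|---|---|---|---|
| tmax | Before Amendment 03 | Time since riluzole dose | Time since study drug dose |
| Ctrough | All patients | End of the riluzole interval | Pre-dose value (SAP abbreviation list), or minimum over the interval after dosing (SAP 5.5.11) |
| Cmax | Before Amendment 03 | Samples around the riluzole peak | Highest of the 1, 3 and 6 h values (1 and 3 h on Day 1) after study drug |
| AUC12 | Before Amendment 03 | Any full 12 h at steady state | Samples at 0, 1, 3 and 6 h, with the pre-dose value reused at 12 h |

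With strict 12-hourly intake, the true steady-state AUC over any 12 h window is the same whatever the phase. Error in AUC12 therefore comes from sparse sampling and irregular intake.

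**2. Size for Ctrough**

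Assumptions, none from the documents: half-life 6 to 12 h, 12-hourly riluzole, and simple exponential decline from 2 h onwards. A sample at time t after riluzole exceeds the 12 h value by the factor 2^((12 − t)/half-life).

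- Pre-dose sample at t = 2 h: 2^(10/12) = 1.78 and 2^(10/6) = 3.17.
- If Ctrough is instead the minimum of the visit's samples, a patient with pre-dose and 1 h samples has a lowest value at t = 3 h: 2^(9/12) = 1.68 and 2^(9/6) = 2.83.
- With the earlier 6 h sample, the lowest value is at t = 8 h: 2^(4/12) = 1.26 and 2^(4/6) = 1.59.

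The choice of definition changes the size of the error but does not remove it.

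**3. All four parameters in a simple model**

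The model is one-compartment, oral, at steady state, with interval τ = 12 h:

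C(t) ∝ ka/(ka − ke) × [e^(−ke·t)/(1 − e^(−ke·τ)) − e^(−ka·t)/(1 − e^(−ka·τ))], with ke = ln 2/half-life.

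Assumed inputs are half-lives of 4, 8 and 12 h and ka of 1 or 3 per h. Samples are at 0, 1, 3 and 6 h after study drug, processed under the SAP 5.5.11 rules with the pre-dose value taken as the trough.

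With simultaneous intake, AUC12 was 0.99 to 1.00 of true, Cmax 0.94 to 1.00 of true, and the trough exact. With riluzole taken from 4 h before to 6 h after study drug, simultaneous intake excluded, the ratios to the true values were:

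| Assumed half-life | Trough | Cmax | AUC12 |
|---|---|---|---|
| 4 h | 1.19–6.38 | 0.37–1.00 | 0.58–1.35 |
| 8 h | 1.09–2.50 | 0.62–1.00 | 0.78–1.18 |
| 12 h | 1.06–1.84 | 0.73–1.00 | 0.85–1.12 |

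Reported tmax was 1, 3 or 6 h after study drug; true tmax was 0.96 to 2.29 h after riluzole. For example, with an 8 h half-life, ka = 1 per h and riluzole taken 2 h early, reported tmax is 1 h. That sample is actually 3 h after riluzole, and true tmax is 2.20 h.

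**The case against.** Several objections have force.

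- **Absence from two documents is not absence from the data.** A reader might infer that riluzole dose times were never captured. The documents do not support that. SAP 8.3 describes an output listing, Protocol 5.11 sends all medications to the eCRF without listing its fields, and a study drug diary would not be expected to cover riluzole. The eCRF and Study Manual were not available. What can be said is that neither the protocol nor the SAP specifies a riluzole time. If times were recorded, the SAP still does not say to use them.
- **The planned interaction assessment is not shown to be compromised.** A reader might infer that it is. Protocol 8.4.7 describes it as CK-2127107 alone against CK-2127107 with riluzole, which can be read as concerning reldesemtiv exposure, and that is correctly timed. SAP 9.1 plans no test, ratio or interval for riluzole exposure; its one modelled comparison concerns edaravone.
- **Riluzole PK is in no objective or endpoint.** This is true, and it limits the consequence to descriptive tables. Randomisation should also balance riluzole timing across dose groups, so the expected harm is wrong labels and lost precision, with no systematic difference between arms.
- **Not every parameter or patient is affected alike.** tmax, Cmax and AUC12 are confined to patients enrolled before Amendment 03, and the true AUC12 does not depend on phase.
- **Patients may take both drugs together.** If they do, the parameters are nearly right, as the model shows. Neither document requires it or says how often it happens.

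What stands is narrower: the SAP names riluzole parameters without saying from which dose they are counted.

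**Conclusion.** The point holds in limited form. As written, riluzole tmax and Ctrough are interpretable only for patients who took riluzole together with study drug, and sampled Cmax is unreliable for the others. AUC12 is less affected in principle, although with sparse sampling the model still put it at 0.78 to 1.18 of true for an 8 h half-life.

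The 1.8- to 3.2-fold overstatement of trough is an illustration. It rests on an assumed half-life, an assumed 12-hourly interval and an assumed 2 h gap between riluzole and the sample. The documents give none of these, nor the share of patients who took the drugs apart.

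The primary and secondary efficacy analyses and reldesemtiv PK are untouched. Severity is minor. Confidence is moderate, because the eCRF and Study Manual could change the picture.

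**What to change.** First check the eCRF and Study Manual for a riluzole dose time at the PK visits. Then amend the SAP before database lock.

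- **Where riluzole dose times exist:** state in SAP 5.5.11 and 9.1 that elapsed time for riluzole runs from the riluzole dose. Make the same clock govern the pre-dose exclusion from Cmax, the 12-hour substitution in AUC12 and the choice of trough sample.
- **Where they do not:** delete riluzole from the tmax, Cmax, AUC12 and Ctrough sentences of SAP 9.1. Report only riluzole concentrations at the nominal study drug sampling times. Protocol 8.4.7 already plans this, naming riluzole for observed concentrations, so the edit stays within the protocol.

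A new eCRF field is probably too late. The SAP is dated 14 December 2018, and the Appendix C pool subtotals already sum to 20 + 53 + 49 + 52 + 61 + 71 + 51 + 36 + 65 = 458 FAS patients, against about 445 planned (the 36 for pool 8 is the sum of its six sites: 10 + 3 + 3 + 5 + 10 + 5). SAP 1 leaves analysis decisions open until lock, so the text edit remains possible.

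The cost is a few words in the SAP and, in the second case, fewer riluzole parameters in the report. No interpretable result that the documents support is lost.

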3.3. Sample Size Consideration

3.3.1. Sample Size Justification

Approximately 445 patients will be randomized. The dropout rate at Visit Week 12 is estimated to be 10%, thus approximately 400 patients are expected to complete 12 weeks of double-blind treatment. The effect of reldesemtiv on the change from baseline to Week 12 in percent predicted SVC will be analyzed using a mixed model for repeated measures (MMRM) with the contrast (-5, -1, 3, 3) to reflect the assumed relationship for the placebo, 300 mg/day, 600 mg/day and 900 mg/day dose groups. The sample size is estimated to provide 90% power to detect 2.75, 5.5 and 5.5 percentage points advantage over placebo in the change from baseline to Visit Week 12 of

percent predicted SVC for the 300 mg/day, 600 mg/day and 900 mg/day reldesemtiv dose groups, respectively. This calculation is based on a two-sided test with alpha set at 0.05 and a common standard deviation (SD) of 14 percentage points.

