3.4. Randomization

Patients will be randomized to receive either one of the three reldesemtiv doses (300 mg/day, 600 mg/day and 900 mg/day TDD) or matching placebo tablets in a ratio of 1:1:1:1. Randomization will be stratified by riluzole and edaravone use status at baseline.

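### The dose-proportionality and steady-state rules in SAP 9.1 read a non-significant slope as support; at the planned size the main risk is rejecting proportionality over a small deviation

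*SAP*

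**What the plan says.** SAP 9.1 sets two decision rules.

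- **Dose proportionality.** "Dose proportionality will be examined using the power model approach based on" Ctrough: ln(Ctrough) is regressed on ln(dose). The rule is: "A tentative conclusion of dose-proportionality will be made if the 90% CI for the slope includes 1".
- **Steady state.** Attainment is to be "verified using a linear regression model for log-transformed trough concentrations on sample collection time by dose group", and "the trough concentrations starting from Week 2 and beyond will be included in the model". Under the schedule these are Weeks 2, 4, 8 and 12. If the 90% CI "of the slope from the model contains zero, steady state will be concluded as attained at no later than Week 2".

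Neither rule has an equivalence region, a limit on CI width or a check on the point estimate. The SAP does not say what is reported when the CI excludes 1 or 0, or which visit's trough enters the power model. Protocol 8.4.7 names neither test, and the prototype code in SAP 13 covers neither model.

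**The concern.** A 90% CI that contains the null value shows only that the data do not contradict the null. When the true deviation is small but not zero, better data make the favourable conclusion less likely. When data are noisy, a real deviation passes. Precision is penalised in one case and imprecision rewarded in the other.

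The steady-state rule has a second gap. The same patients supply up to four troughs each, and the text names no term for the patient. If the model is fitted as ordinary regression, between-patient variance goes into the slope's standard error. The interval is then wider than a 90% interval should be, and containing zero becomes easier.

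At stake is whether two stated PK conclusions mean what they say. Exposure is a secondary objective, and characterising PK at three dose levels is a PK/PD objective (Protocol 2.2 and 2.4).

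**Working it through.** **Sample size.** Allocation is to three doses "or matching placebo tablets in a ratio of 1:1:1:1", and "approximately 400 patients are expected to complete 12 weeks of double-blind treatment", so n = 100 per dose. The only stated power is for the primary contrast, and it reproduces. The contrast is -5(0) - 1(2.75) + 3(5.5) + 3(5.5) = 30.25. Its SE is 14 × sqrt(44/100) = 9.29, and power = Φ(30.25/9.29 - 1.96) = 90.3%, against 90% stated. The PK rules have no stated power or precision target.

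**Variability.** The documents give no CV for Ctrough. Protocol 3.3 gives predicted Cmax CVs of 44.1% and 35.9%. I assume 36-44% for Ctrough, with 100% as a noisy case, and one trough per patient.

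**Proportionality.**

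- ln(300), ln(600), ln(900) = 5.704, 6.397, 6.802, mean 6.301. Sxx = 0.357 + 0.009 + 0.251 = 0.617.
- SD on the log scale = sqrt(ln(1 + CV²)); SE(slope) = SD/sqrt(100 × 0.617).
- P(CI includes 1) = Φ(1.645 - δ/SE) - Φ(-1.645 - δ/SE), where δ = true slope - 1.
- A slope of 1.10 gives 3^0.10 = 1.116, a 12% excess at 900 relative to 300 mg/day. A 25% excess is δ = ln(1.25)/ln(3) = 0.203.

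| CV | log SD | SE | CI includes 1, slope 1.00 | slope 1.10 | slope 1.203 |
|---|---|---|---|---|---|
| 36% | 0.349 | 0.0444 | 90% | 27% | 0.2% |
| 44% | 0.421 | 0.0535 | 90% | 41% | 1.6% |
| 100% | 0.833 | 0.106 | 90% | 75% | 39% |

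So at CV 36-44% a slope of 1.10 has a CI excluding 1 in 59-73% of trials.

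The dependence on precision is clearest at slope 1.05 and CV 44%. The chance of including 1 is 89% with 10 per dose, 76% with 100 and 9.5% with 1000.

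**Proportionality with limits.** Require the 90% CI to lie within 1 ± 0.203, about 0.80 to 1.20. At a true slope of 1, P(pass) = 2Φ(0.203/SE - 1.645) - 1. This is 99.7% (CV 36%), 97% (CV 44%) and 21% (CV 100%). At slope 1.203 it is at most 5%. At slope 1.05 and CV 44% it rises with data: 18% (25 per dose), 89% (100), 100% (1000).

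**Steady state.** I assume log SD 0.4-0.6 between patients and 0.3 within.

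- Weeks 2, 4, 8, 12 have mean 6.5, so the time sum of squares per patient is 20.25 + 6.25 + 2.25 + 30.25 = 59.
- With complete data the slope's true SE is 0.3/sqrt(59n). Ordinary regression reports sqrt(between² + within²)/sqrt(59n), larger by 0.500/0.3 = 1.67 to 0.671/0.3 = 2.24.
- With no drift, P(interval contains 0) = 2Φ(1.645 × 1.67) - 1 = 99.4%, up to 2Φ(1.645 × 2.24) - 1 = 99.98%, whatever n is. The nominal figure is 90%.
- A patient effect alone restores 90% but exposes the first fault. With no drift, at least one of three dose groups fails in 1 - 0.9³ = 27% of trials. For a 5% rise over the 10 weeks, δ/SE = (ln(1.05)/10)/(0.3/sqrt(5900)) = 1.25, so zero is excluded about 35% of the time in one group.

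**The case against.** Much of the case on the other side stands.

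- For proportionality the SAP promises only a tentative conclusion. That softens the label but leaves the rule unchanged. No consequence is stated when the CI excludes 1, so calling that a failure is an inference.
- The results stay visible: SAP 9.1 also plans geometric means, geometric CVs, plots over time and parameter summaries by dose.
- At a true slope of exactly 1 the rule passes 90% of the time at any sample size. At the slope implied by the protocol's Cmax predictions, ln(5543/1789)/ln(3) = 1.029, it passes 83-85% of the time with 100 per dose.
- The absence of a patient effect is read from silence. Later in SAP 9.1, the edaravone comparison is also called a linear regression model and is given an unstructured covariance matrix. At most the steady-state model is unspecified, and the 99% figure applies only if it is fitted as ordinary regression.
- No equivalence limits appear in the documents.

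A reader might infer three stronger points, which the documents do not support.

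- *That steady state would be declared despite harmful drift.* As written, a 10% rise would often pass. But with the illustrative ratio limits of 0.80-1.25 it should usually pass: using the slope over 10 weeks, SE = 10 × 0.3/sqrt(5900) = 0.039, and Φ((ln 1.25 - ln 1.10)/0.039 - 1.645) is about 95%. The half-life is about 12 hours (Protocol 1.3), so Week 2 is 336/12 = 28 half-lives in. Later drift would mainly reflect adherence or other change, with negligible residual accumulation.
- *That these rules decide Phase 3 doses.* Protocol 3.3 says that information from the study will guide dose selection. It ties nothing to either rule, and the PK/PD analyses in SAP 9.2 use measured concentrations or concentration bins.
- *That efficacy conclusions are touched.* Both rules lie outside the testing sequence in SAP 7.4.

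**Conclusion.** The concern holds as a minor point about two PK decision rules. Both treat failure to reject as support, and nothing elsewhere in the documents supplies a margin.

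At about 100 per dose and the borrowed Cmax CVs, the practical risk for proportionality is false failure: 59-73% at a 12% excess. False passes at a 25% excess are 0.2-1.6%. They become material only if troughs vary much more than Cmax or many are missing.

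For steady state, the unstated error structure could leave the 90% interval miscalibrated, at 99% or more coverage under no drift, if ordinary regression is used with the assumed variances. The size of that effect depends on those variances; its direction does not.

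**What to change.** Amend SAP 9.1 before database lock:

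1. Conclude proportionality only if the whole 90% CI for the slope lies inside preset limits, for example 0.80-1.20, that is 1 ± ln(1.25)/ln(3). State which visit's Ctrough enters.
2. Fit log troughs by dose group with a random patient effect. Conclude steady state only if the 90% CI for the Week 12/Week 2 trough ratio lies inside preset limits, for example 0.80-1.25. Make both changes together, since a patient effect alone keeps the contains-zero rule and its false failures.
3. Otherwise report the result as inconclusive, and give the estimate and CI in every case.

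The limits are illustrative assumptions for the sponsor to confirm.

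The cost is SAP wording and a small programming change. The downside is that noisy data yield an inconclusive result: at a CV of 100% only about 21% of trials of a truly proportional drug would pass.
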